My prior work has shown that challenging maladaptive beliefs about memory ability can lead to reduction in compulsive checking symptoms (Alcolado & Radomsky, 2016). We conducted a pilot study to develop and test the efficacy of an intervention designed to target maladaptive beliefs about memory (Alcolado & Radomsky, 2016). After just two sessions of this specific cognitive intervention for checking (CBT-C), the active treatment group, as compared to a waitlist control, had significant decreases in maladaptive beliefs about memory, and importantly, also exhibited significant decreases in checking symptomatology (with large effect sizes, all η_p^2 s > .32). Critically, the decreases in those maladaptive beliefs predicted symptom improvement. **Thus, there is good preliminary evidence that such a targeted, theory-based approach is useful for the treatment of obsessive-compulsive checking. A number of pertinent questions remain, however.** At the forefront of these is whether such a brief intervention is durable and whether, for certain individuals, it is more effective than treatment as usual.

Study Objectives:

- 1. Replication of previous pilot study findings with a larger sample:** Pilot testing (N = 24) was promising (Alcolado & Radomsky, 2016). This treatment was effective at significantly reducing global checking symptomatology and average daily time spent checking, with large effect sizes. Thus, the next logical step is to replicate these findings on a larger scale (N = 50).
- 2. Compare the effectiveness of the treatment to an active treatment:** The pilot study used a waitlist control group against which the treatment (CBT-C) effects were compared. Therefore the current proposal aims to use a more active control condition. A treatment as usual (TAU) approach was chosen as this type of control is most applicable where one is trying to determine whether the therapy adds anything of benefit to existing interventions (for a review see Mohr et al., 2009).
- 3. Determine the long-term durability of the treatment effects:** Another equally important step in this replication and extension study is to ascertain whether the effects of the intervention are durable beyond the end of treatment. A six-month follow-up assessment will therefore be administered.

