- 4. Determine for whom the intervention is effective:** This novel CBT intervention for checking (CBT-C) focuses on identifying and challenging maladaptive beliefs about memory, with the aim to increase patients' confidence in their memory for checking situations. In the preliminary treatment investigation, maladaptive beliefs about memory decreased significantly across treatment, and were predictive of decreased checking behaviours at post-treatment (Alcolado & Radomsky, 2016). However, it remains unclear for whom this intervention is most effective. Are all individuals with compulsive checking plagued by maladaptive beliefs about memory, and do patients need to endorse these beliefs in order for this treatment to be effective? These questions will also be examined in this investigation, where the larger sample size will allow for comparisons based on patients' degree of endorsement of maladaptive beliefs about memory.

Hypotheses:

Following directly from the project's objectives, the hypotheses are **(1)** that the treatment (CBT-C) will be effective, in replication of a previous pilot treatment; **(2)** this brief intervention will be more effective than the comparison condition (TAU); **(3)** the effects will be maintained at 6-month follow-

up; and that (4) although the treatment will be effective for all, it will be most effective for those patients with high pre-treatment levels of maladaptive beliefs about memory.

Design/Methodology

Participants:

Participants (N = 50): n = 25 in CBT-C, and n = 25 in TAU; allowing for the testing of an additional 5 participants [predicting an approximate 10% drop-out rate as was seen in the pilot study]) will take part. This sample size is reasonable given the number of OCD referrals our clinic typically receives in a year (approximately N = 50) in conjunction with the active recruitment we will do through the community support groups, allowing for ineligible participants and study attrition. This sample size is also adequately powered for the analyses (see Power Analyses and Statistical Plan, below). Participants will come from one of two sources, either our Anxiety Disorders Clinic or community (see Recruitment, below).

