Compensation: Participants will be offered \$10 at the end of each assessment visit (for a maximum of \$30 per participant), as a monetary compensation for participants time and efforts, as well as to offset the costs of transportation for their appointments. They will not be offered compensation for their treatment visits. Compensation will be offered in-person, or, if a participant attends online visits, will be provided by mail.

Timeline:

Time point	Phone Screen	Pre-treatment Assessment	Treatment Week 1	Treatment Week 2	Post-treatment Assessment	6-mo. follow-up & debrief
Condition						
A) CBT-C	✓	✓	✓	✓	✓	✓
B) TAU	✓	✓	×	×	✓	✓

✓ = Study visit at this time point

× = No study visit at this time point

Statistical Plan:

Intent-to-treat (ITT) analyses will be conducted in order to accurately depict the progression of all participants through this treatment. As such, if there is drop-out, the last observation point for those participants will be carried forward for all subsequent missing data points of interest. To test **hypotheses 1, 2, and 3** (1 - that the treatment be effective, 2 – as compared to the control group, and 3 – that its effects last over the follow-up period), a mixed-model ANOVA will be conducted. The between-participants independent variable will be treatment condition (CBT-C vs. TAU), and the within-participants independent variable will be time point (pre-treatment, post-treatment, and 6-month follow-up). The dependent variable will be the checking subscale of the VOCI. A similar analysis using average daily time spent checking per week from the daily diaries as a dependent variable, as an alternate measure of checking.

A linear regression will be conducted to test **hypothesis 4** (that the extent to which maladaptive beliefs about memory are endorsed affect outcome). Pre-treatment BAMI total score will be entered as the predictor variable. The criterion variable will be a change score that subtracts pre-treatment VOCI score from post-treatment VOCI score. All analyses will be conducted using SPSS statistical software.

Budget details and available resources:

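### Last observation carried forward enters zero relapse for anyone lost after the post-treatment visit, which tilts the 6-month durability test (hypothesis 3) toward maintenance

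*Combined protocol and SAP*

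**What the plan says.** Under Statistical Plan, the stated aim is "Intent-to-treat (ITT) analyses will be conducted in order to accurately depict the progression of all participants through this treatment". For drop-outs, "the last observation point for those participants will be carried forward for all subsequent missing data points of interest". A single analysis covers the first three hypotheses: "a mixed-model ANOVA will be conducted", with condition (CBT-C, TAU) between participants and time (pre-treatment, post-treatment, 6 months) within. The outcome is the VOCI checking subscale, and a similar analysis uses daily time spent checking. Hypothesis 3 is worded there as "that its effects last over the follow-up period". Study Objectives gives the purpose of the 6-month visit: to "ascertain whether the effects of the intervention are durable beyond the end of treatment".

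The Timeline shows no assessment between post-treatment and 6 months. Under Participants, the sample of 25 per arm is set while "predicting an approximate 10% drop-out rate as was seen in the pilot study". The plan states no other missing-data method, no missingness assumption, no sensitivity analysis, and no specific contrast of post-treatment with 6 months.

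**The concern.** A missing 6-month score can be filled only from post-treatment or, failing that, from pre-treatment. In the first case the participant contributes a post-to-6-month change of exactly zero. Because no contrast or margin is specified, hypothesis 3 would in practice be supported by finding no loss between those visits. Shrinking that change toward zero therefore helps the hypothesis whenever some relapse occurs.

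Loss could also depend on outcome. The section on potential harm says that participants who do not respond or who worsen will be reminded that they may leave to seek other treatment. That is a route from deterioration to a missing score.

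The same rule freezes TAU scores. Under Treatment as Usual, clinic patients keep their place on the waiting list and may be offered service during follow-up. If TAU participants who are lost have in fact improved, the 6-month difference between arms is overstated.

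**Working it through.** **The plan's own sample size.** The protocol gives N = 44 for the ANOVA, with a medium effect and high power but no numerical values. Assume f = 0.25, alpha = 0.05, correlation between visits 0.5 and target power 0.95. For the condition-by-time interaction, lambda = f² × N × m / (1 - rho) = 0.0625 × 44 × 3 / 0.5 = 16.5 on 2 and 84 degrees of freedom. Power is 0.956, so 44 is reproduced. Allowing for 10% drop-out, 44 / 0.90 = 48.9, or 49, which agrees with 50. This point does not change the sample size.

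**Random loss after post-treatment.** Let R be the true mean post-to-6-month relapse and d the share of an arm lost. Those observed average R and those filled contribute 0, so the expected estimate is (1 - d) × R. R = 0.5 SD is an assumption. The 10% is the protocol's figure, here placed wholly after post-treatment; 20% and 30% are assumptions.

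| d | Filled, of 25 | Estimate (SD) | Understatement (SD) |
|---|---|---|---|
| 10% | 2.5 | 0.90 × 0.5 = 0.45 | 0.05 |
| 20% | 5 | 0.80 × 0.5 = 0.40 | 0.10 |
| 30% | 7.5 | 0.70 × 0.5 = 0.35 | 0.15 |

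**Precision.** One arm was simulated with n = 25, correlation 0.6 and R = 0.5 SD. With 5 lost at random, carrying forward gives 0.40 SD with a standard error of 0.163. Complete data on all 25 would give 0.177, and the 20 observed cases give 0.50 SD with 0.197. The filled analysis thus claims more precision with five scores missing than with none. Coverage of its 95% interval is 91%, and 82% with 8 lost; observed cases hold 95%. At 10% loss the gap is small, about 0.170 against 0.186.

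**Loss driven by relapse.** A second simulation (n = 25, correlation 0.5, R = 0.5 SD, paired t-test) made the chance of loss rise with the exponential of the individual's change. Power to detect the relapse with full data is about 0.67.

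| Lost of 25 | Random loss: carried-forward estimate, power | Relapse-driven loss: carried-forward estimate, power | Relapse-driven loss: observed cases only, estimate |
|---|---|---|---|
| 2 | 0.46, 0.63 | 0.39, 0.52 | 0.42 |
| 5 | 0.40, 0.57 | 0.25, 0.32 | 0.31 |
| 8 | 0.34, 0.50 | 0.13, 0.16 | 0.19 |

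The last column also falls short of 0.5: dropping the filled values does not by itself cure this kind of loss.

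**An extreme case.** Assume a 1.0 SD gain at post-treatment, relapse of 0.5 SD in those retained and 1.0 SD (full) in those lost. True relapse is 0.5(1 - d) + 1.0d = 0.55, 0.60 and 0.65 SD at 10%, 20% and 30% loss. Carrying forward gives 0.45, 0.40 and 0.35, short by 0.10, 0.20 and 0.30 (18%, 33% and 46%). A likelihood-based model gives about 0.50 throughout, short by 0.05, 0.10 and 0.15. So half of the error in this case belongs to the loss mechanism and would remain under the better model.

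**Loss before post-treatment.** The pre-treatment score fills both later visits, so all change is zero, including the hypothesis 4 change score. In CBT-C this records no benefit, which is usually conservative for hypotheses 1 and 2.

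**The case against.** The strongest reply is about size. The only drop-out figure in the documents is about 10%, or two or three people per arm. At that rate the random-loss bias is about 0.05 SD against a standard error of about 0.17, and the other 22 or 23 participants supply real 6-month data. Several features also support retention: payment at each assessment, online visits, clinic patients keeping their waiting-list place, and follow-up by the principal investigator if the assistant is unavailable. All of this stands. The calculations also follow one arm, not the planned two-arm interaction test, so the effect on that test is not quantified.

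A reader might go further and infer any of the following. The documents do not support them.

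- The rule settles hypothesis 3 by itself. It affects only the filled share.
- A third to nearly a half of relapse would be hidden. That needs 20% to 30% loss and full relapse in everyone lost, neither of which is in the documents, and half of that error would survive the recommended model.
- Loss will concentrate in the 6-month gap. This is plausible, since the 10% comes from a pilot of a two-session treatment and no 6-month attrition is reported, but nothing establishes it.
- Hypotheses 1 and 2 are biased in an unpredictable direction. For early loss in CBT-C the usual direction is conservative.

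What the reply does not answer is direction. When relapse occurs, values filled after post-treatment move the durability estimate toward the hypothesis, and the plan has no analysis that would show it.

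**Conclusion.** The concern holds at a moderate size. For anyone lost after post-treatment, the plan supplies as data the maintenance that hypothesis 3 is meant to test. With an assumed relapse of 0.5 SD and random loss, relapse is understated by about 0.05 SD at 10% and by 0.10 to 0.15 SD at an assumed 20% to 30%, and by more if relapse drives loss. The reported standard error is too small for the information collected, slightly at 10% and clearly at 20% or more. Frozen TAU scores may also overstate the 6-month difference if TAU participants improve through service received during follow-up. An intention-to-treat analysis does not require this rule.

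**What to change.** Replace the carry-forward rule and the ANOVA on filled data with a likelihood-based linear mixed model for repeated measures. Use SPSS MIXED with arm, visit and arm-by-visit, unstructured covariance, REML and small-sample degrees of freedom, on all observed scores of all randomised participants. Use the same approach for daily time spent checking. State how a missing post-treatment score is handled in the hypothesis 4 change score.

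For hypothesis 3, report the post-treatment versus 6-month contrast in each arm with a confidence interval.

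Because the mixed model does not cure relapse-driven loss, add one sensitivity analysis in which CBT-C participants missing at 6 months return to their pre-treatment level, by multiple imputation. In the extreme case above this would give (1 - d) × 0.5 + d × 1.0, the true value. Imputing from TAU is less suitable: TAU participants may receive service during follow-up, so their scores need not represent relapse.

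The cost is SAP wording and a little analysis work in software already budgeted, with no extra data. Confidence intervals will be somewhat wider than under the current rule. The budget section reports three participants completed and 47 still to be recruited, so the change can be made before nearly all the data exist.

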Inclusion criteria are that participants must be age 18 or older, with a diagnosis of OCD and clinically significant levels of compulsive checking. This is defined as being able to meet the diagnostic criteria for OCD according to the Diagnostic and Statistical Manual of Mental Disorders, 5th Edition (DSM-5; American Psychiatric Association, 2013) based solely on checking symptoms. Other OCD symptoms may be present and checking does not need to be the primary symptom. This study will be offered through online video conferencing platforms or in-person appointments to adhere to pandemic restrictions and maximum safety. If pandemic restrictions are in place, participants must be available for appointments using an online video conference platform such as Zoom, Microsoft Teams, or Doxy.

Exclusion criteria include active suicidality, psychosis, mania, or a substance use disorder that would interfere with participation in the treatment. Participants do not have to be treatment or CBT naïve, and can be medicated, as we are interested in a real-world sample. This information will be collected and tracked in case any differences become relevant for analyses.

Power analyses conducted using G*power (Faul, Erdfelder, Lang, & Buchner, 2007) indicate the sample size of 50 participants will provide more than adequate power to conduct all analyses (see Statistical Plan, below). For the ANOVAs, assuming a medium effect size, 2 conditions, 3 time points, and requiring a high level of power, an N of 44 is needed. For a linear regression with one predictor, with similar effect size and power, N = 43 is needed.

Materials:

Measures: These will include a **background information** form (including age, sex, level of education, marital status, and work status). **The MINI International Neuropsychiatric Interview** (Sheehan et al., 1998) Version 6.0 will be administered to diagnose presence of OCD and any other co-morbid conditions according to the. OCD severity will be assessed using the gold standard **Yale-Brown Obsessive Compulsive Scale** (Y-BOCS; Goodman et al., 1989a). **Validated self-report questionnaires assessing OCD symptoms** (the Vancouver Obsessional Compulsive Inventory [VOCI]; Thordarson et al., 2005), **beliefs** (Obsessive Beliefs Questionnaire [OBQ]; OCCWG, 2005), and associated **affective symptoms** (Depression Anxiety Stress Scale, DASS; Lovibond & Lovibond, 1995) will be administered. To assess beliefs about memory, the new **Beliefs about**

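### Hypotheses 1 to 3 share one 2 x 3 ANOVA with no term or contrast assigned to any of them, and its interaction cannot show that benefit is kept at 6 months

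*Combined protocol and SAP*

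**What the plan says.** The Hypotheses section makes three separate claims about CBT-C: that it is effective, that "this brief intervention will be more effective than the comparison condition (TAU", and that its effects persist to 6 months. The Statistical Plan restates the third as "that its effects last over the follow-up period".

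All three go to one analysis: "a mixed-model ANOVA will be conducted. The between-participants independent variable will be treatment condition (CBT-C vs. TAU". The repeated factor is described next, and baseline is one of its levels: "the within-participants independent variable will be time point (pre-treatment, post-treatment, and 6-month follow-up". On the outcome it says: "The dependent variable will be the checking subscale of the VOCI". A similar analysis is planned for diary checking time.

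The plan names no main effect, interaction, planned contrast or follow-up comparison for any of the three hypotheses. It gives no significance level, no testing order, no baseline covariate and no criterion for an effect having lasted. The sample-size paragraph under Participants sizes the ANOVAs at N = 44, "assuming a medium effect size, 2 conditions, 3 time points" and a high level of power, also without naming the effect being powered.

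**The concern.** A 2 x 3 mixed ANOVA yields three F-tests, and none of them corresponds one-to-one with the three claims.

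- **Time** compares visits averaged over both arms. It includes whatever TAU patients gain and any regression to the mean, so it is not an effect of CBT-C. The Interventions section says TAU may include group psychoeducation, medication and independent therapy, so improvement in both arms is plausible.
- **Condition** compares the arms averaged over all three visits, including the baseline, where randomisation makes the expected difference zero.
- **Condition by time** asks whether the arms differ in their pattern over the visits. It does not say at which visit they differ or in whose favour.

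The third Study Objective is durability. If no listed test separates a lasting benefit from one that has gone by 6 months, the trial could be analysed exactly as planned and leave that objective unanswered.

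**Working it through.** **Inputs.** From the documents: N = 50 (25 per arm), 3 visits, a medium effect, N = 44. Not in the documents and therefore assumed: medium means f = 0.25; alpha = 0.05 (two-sided for t-tests); equal correlation rho between visits, with sphericity; arm difference d in SD units. The values of d and rho are varied.

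**1. The plan's own figure.** For the within-subject or interaction F-test, lambda = f² × N × 3 / (1 − rho), with df 2 and 2(N − 2). At N = 44 and rho = 0.5, lambda = 0.0625 × 44 × 3 / 0.5 = 16.5 and power is 95.6%. So N = 44 reproduces at 95% power for the interaction or the time effect. The condition main effect would need N = 142. For a difference of 0 at baseline and d at both later visits, f = d/√18, so f = 0.25 means d = 0.25 × √18 = 1.06 SD.

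**2. Can the interaction detect maintenance?** With n = 25 per arm, lambda = (n/2) × S / (1 − rho), where S is the sum of squares of the three arm differences about their mean.

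| Profile (baseline, post, 6 months) | S | lambda at d = 0.8, rho = 0.5 | Power |
|---|---|---|---|
| Kept: 0, d, d | (2/3)d² | 12.5 × 0.4267 / 0.5 = 10.67 | 82.9% |
| Lost: 0, d, 0 | (2/3)d² | 10.67 | 82.9% |
| Late only: 0, 0, d | (2/3)d² | 10.67 | 82.9% |

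S is the same in all three rows, so power is equal at any d and rho under this correlation structure. Simulation (10,000 trials each) gave 83.3% for kept and 83.4% for lost. In the same trials the baseline-adjusted arm difference at 6 months was significant in 88.7% (kept) and 4.9% (lost).

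**3. Time main effect.** Suppose both arms improve by 0.5 SD and hold it, with no advantage for CBT-C. Then lambda = 50 × (2/3) × 0.25 / 0.5 = 16.67, and the time effect is significant 96% of the time at rho = 0.5.

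**4. Condition main effect.** The difference is diluted to 2d/3, with variance (1 + 2rho)/3 per patient. At d = 0.8 and rho = 0.5 the noncentrality is 0.533 / √(2 × 0.667/25) = 2.31 and power is 61.9%.

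**5. Power of the proposed contrast.** For the adjusted difference at post-treatment, the noncentrality is d / √(2(1 − rho²)/25) on 47 df. At d = 0.5 and rho = 0.5 this is 0.5 / √0.06 = 2.04.

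| d | rho | Omnibus interaction | Adjusted difference at post-treatment |
|---|---|---|---|
| 0.5 | 0.5 | 41.9% | 51.6% |
| 0.5 | 0.7 | 63.7% | 67.9% |
| 0.5 | 0.8 | 81.9% | 82.3% |
| 0.8 | 0.3 | 68.0% | 82.7% |
| 0.8 | 0.5 | 82.9% | 89.2% |
| 0.8 | 0.7 | 96.9% | 97.2% |
| 0.8 | 0.8 | 99.7% | 99.6% |
| 1.06 | 0.5 | 97.6% | 98.9% |

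**6. Non-significance as evidence of maintenance.** For a true 0.3 SD relapse (an illustrative size) in 25 CBT-C patients, a paired t-test has noncentrality 0.3 / √(2(1 − rho)/25). Power is 30% at rho = 0.5 and 46% at 0.7, so the relapse is missed 70% and 54% of the time.

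**The case against.** The strongest reply is that the model is sound and only its reporting is under-specified. Much of that stands.

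- A reader might infer that none of the three hypotheses is properly tested. That goes too far. The interaction is a legitimate test of differential change, with a simulated type I error of 4.9%, and it serves hypothesis 2. Being non-directional is no fault; the replacement is two-sided too. Contrasts at each visit could also be drawn from the same ANOVA.
- A reader might infer that the sponsor will claim success from whichever F-test is significant. The documents do not say so, and the sizing points away from the condition main effect (N = 142, against the stated 44). They do leave time and interaction both open.
- A reader might infer that the plan will declare maintenance from a non-significant post-to-6-month change. It states no such rule. The gap is that no rule is given; step 6 only shows why that one should not fill it.
- A reader might infer a substantial loss of power from treating baseline as an outcome. The loss depends on assumed values, and part of it comes from the 2-df test. A 1-df contrast of the mean of both later visits minus baseline keeps baseline as an outcome and has 52% power at d = 0.5, rho = 0.5 and 73% at rho = 0.7, against 52% and 68% for the adjusted post-treatment difference.

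What the reply does not meet is hypothesis 3. The stated test responds identically to lasting benefit and to complete loss, and the plan names no contrast that would tell them apart.

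**Conclusion.** The concern holds in a limited form. No term or contrast is assigned to hypotheses 1 to 3. For hypothesis 2 the interaction is valid but unfocused. For hypothesis 1 the time effect does not isolate CBT-C. For hypothesis 3 the omnibus interaction cannot do the job: its power is equal for a kept, a lost and a late-only benefit. The figure of 82.9% rests on d = 0.8 and rho = 0.5; the equality holds for any d and rho, given equal correlations between visits.

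Power is a secondary argument. Over the values examined, the gain from the adjusted post-treatment difference runs from about 15 points (d = 0.8, rho = 0.3) to none (d = 0.8, rho = 0.8), and is 1.3 points at the 1.06 SD that reproduces N = 44. The case for change rests on stating which comparison answers which hypothesis and on making hypothesis 3 testable.

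**What to change.** Replace the omnibus test with named comparisons from one repeated-measures model of VOCI checking at post-treatment and 6 months, adjusted for baseline VOCI checking:

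1. **Primary (hypotheses 1 and 2):** the CBT-C minus TAU difference at post-treatment, two-sided 5%.
2. **Hypothesis 3:** the same adjusted difference at 6 months, tested at two-sided 5% only if the first is significant.
3. **Supporting:** the CBT-C change from post-treatment to 6 months with its 95% CI. Do not conclude that effects were maintained because this change is non-significant. Within-arm changes are descriptive.

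Adjustment for recruitment source (clinic or community) is optional. The plan's last-observation-carried-forward rule needs to be read alongside item 3: a post-treatment score carried to 6 months gives a change of zero by construction.

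**Cost.** SAP wording only. Baseline VOCI is already collected under Assessments, and no extra patients or visits are needed. The budget section records three completers and 47 participants still to be recruited. The downside is small: the 6-month test depends on the post-treatment result, so success on both cannot be likelier than success on the first, and a benefit that appears only late would not be formally tested. Splitting alpha instead (0.025 each) avoids the gate but takes the adjusted contrast to 82.6% at d = 0.8, rho = 0.5, about the same as the omnibus test's 82.9%.

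### Diary checking time, a zero-bounded and possibly skewed outcome, gets the VOCI's 2 x 3 ANOVA with no baseline adjustment and no stated scale; a pre-specified baseline-adjusted comparison would be safer

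*Combined protocol and SAP*

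**What the plan says.** Under Statistical Plan, hypotheses 1 to 3 are tested as follows: "a mixed-model ANOVA will be conducted", with condition (CBT-C, TAU) between participants and three time points within. The first dependent variable is the VOCI checking subscale. Diary time follows in one sentence: "A similar analysis using average daily time spent checking per week from the daily diaries as a dependent variable", "as an alternate measure of checking". Nothing is said about transformation, zero minutes, assumption checks, adjustment for the pre-treatment value or a fallback.

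The power statement, under Participants, is generic: "Power analyses conducted using G*power", "assuming a medium effect size, 2 conditions, 3 time points", and "requiring a high level of power, an N of 44 is needed". Allocation is "n = 25 in CBT-C, and n = 25 in TAU". Checking time has no power assumptions of its own, although the same paragraph says that 50 participants are enough for all analyses. Study Objectives reports that the pilot (N = 24) reduced checking time significantly with a large effect. It gives no mean, SD, skewness or scale of analysis.

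**The concern.** Minutes per day cannot fall below zero, and a treatment that works pushes them towards zero. If it cuts time roughly in proportion, the spread shrinks with the mean. A few participants who check for hours can then dominate both the arm means and the error term.

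The planned test is also a 2-df interaction across three visits. It does not use the pre-treatment value as a covariate, although that value is collected and already enters the model. With 25 per arm, both features can cost power.

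At stake is the second checking outcome. It is one of the two outcomes on which Study Objectives says the pilot succeeded and which this trial sets out to replicate. A real proportional reduction could go undetected. If the scale is chosen only after the data are seen, the choice itself becomes open to question.

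**Working it through.** **1. The plan's own figure.** The documents give 2 conditions, 3 time points, a medium effect and N = 44. Assumed, because not stated: f = 0.25, alpha 0.05, correlation 0.5, sphericity. For the within-between interaction:

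- lambda = f² x N x m / (1 − rho); df1 = (k − 1)(m − 1) = 2; df2 = (N − k)(m − 1).
- N = 44: lambda = 0.0625 x 44 x 3 / 0.5 = 16.5, df 2 and 84, power 0.956.
- N = 50: lambda = 0.0625 x 50 x 3 / 0.5 = 18.75, df 2 and 96, power 0.976.

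So 44 is reproduced if high power means 0.95. For a roughly normal outcome with that effect, the planned test has ample power.

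**2. Distributions assumed for checking time.** None is given, so a range is shown. For lognormal data, CV = sqrt(exp(s²) − 1) and skewness = (exp(s²) + 2) x CV. With an illustrative median of 60 minutes, the middle 95% is 60 x exp(±1.96 s).

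| Log-SD s | CV | Skewness | Middle 95% (min) |
|---|---|---|---|
| 0.5 | 0.53 | 1.8 | 23 to 160 |
| 0.8 | 0.95 | 3.7 | 13 to 288 |
| 1.0 | 1.31 | 6.2 | 8 to 426 |

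Without zeros, the median affects none of the tests in step 3, because rescaling all values changes neither F nor ranks.

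**3. Simulated power.** Settings: 25 per arm, CBT-C halves time at both later visits, correlation about 0.55, no zeros. The planned test is the condition x time F on raw minutes. Each ANCOVA compares arms at one follow-up visit, adjusted for the pre-treatment value.

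| Setting | Planned ANOVA | Raw ANCOVA | Rank ANCOVA |
|---|---|---|---|
| Lognormal, 0.5 | 96% | 100% | 100% |
| Lognormal, 0.8 | 58% | 83% | 93% |
| Lognormal, 1.0 | 36% | 58% | 78% |
| Gamma, shape 4 | 99% | – | 100% |
| Gamma, shape 2 | 83% | – | 95% |
| Gamma, shape 1 | 52% | – | 67% |

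Under gamma skew, raw ANCOVA also beat the plan and did at least as well as ranks. With normal data, the planned test had 75% and the rank test 78%.

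**4. Splitting the gain.** In the lognormal rows the total is 4, 35 and 42 points. Moving from the planned ANOVA to raw ANCOVA gives 100 − 96 = 4, 83 − 58 = 25 and 58 − 36 = 22. Moving on to ranks adds 0, 93 − 83 = 10 and 78 − 58 = 20. The split depends on the order. If the ANOVA is kept and only the scale changed, with correlation 0.5 and log-SD 0.8, power is 54% raw against 89% on logs.

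**5. Zeros.** With 5% zeros, separate runs gave these ranges:

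| Log-SD | Planned ANOVA | Rank ANCOVA |
|---|---|---|
| 0.5 | 87–92% | 99% |
| 0.8 | 47–52% | 82–85% |
| 1.0 | 29–32% | 65–70% |

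The ANOVA on log(minutes + 1) is unreliable here. At log-SD 0.5 with 5% zeros it had 63%, below the plan's 92% in the same run. At log-SD 0.8, where 10% of CBT-C participants alone reached zero after treatment, it had 97%. Its behaviour depends on where the zeros fall.

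**6. Type I error.** With no effect, the raw ANOVA rejected in about 3.5% to 4.9% of trials and the rank ANCOVA in about 4.8% to 5.5%.

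Dropout (about 10% expected) and carrying the last observation forward were not modelled.

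**The case against.** **Nothing shows strong skew.** This stands. The documents give no distribution, and averaging over a week may reduce skew. At log-SD 0.5 the planned test loses little (96% against 100%). Changing only the scale of the ANOVA under gamma skew recovers only about 0 to 17% in relative terms. A reader might infer that the raw scale is known to cost a third or more of the power. The documents do not support that: it needs an assumed log-SD of about 0.8 or more, and much of the gain over the plan comes from baseline adjustment.

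**The range of severity is limited.** A reader might take "Other OCD symptoms may be present and checking does not need to be the primary symptom" to mean that any severity is eligible. It does not. The same criteria require clinically significant checking that meets the OCD diagnosis on checking symptoms alone, so there is a floor at entry.

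**The plan does not say untransformed.** Correct. Raw minutes are the natural reading of a similar analysis, but this is an inference from silence. The defect is that the scale is not stated.

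**The pilot found a large effect with N = 24.** True, but against a waitlist and with the scale of analysis not given. It does not show that the planned test is adequate against TAU.

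**A visit-by-visit comparison drops the time factor and adds a second test.** This stands, and the fix allows for it: one visit is named as the main comparison and the time-factor ANOVA is kept.

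**Conclusion.** The point holds as a matter of power and pre-specification. The plan gives a zero-bounded outcome the VOCI's ANOVA with no scale and no baseline adjustment, and a baseline-adjusted test did better in every setting tried. The size is a range: about 4 points at log-SD 0.5, 35 at 0.8 and 42 at 1.0, and 1, 12 and 15 points under gamma skew of shape 4, 2 and 1. These figures assume 25 per arm, time halved and correlation about 0.55. At log-SD 0.8, a higher correlation makes the planned test stronger: in a separate run with correlation 0.7 it had 73%.

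The point does not extend to validity. False positives are not inflated, and the VOCI analysis is unaffected. A reader might also infer that a non-significant diary result would contradict a significant VOCI result. It would not, because diary time is named only as an alternate measure and could miss significance through low power.

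**What to change.** In the Statistical Plan, replace the sentence on diary time with text to this effect:

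> Average daily checking minutes will be compared between arms at post-treatment and at 6 months by ANCOVA, adjusting for pre-treatment minutes. The test will be carried out on ranks (rank of follow-up minutes on arm and rank of pre-treatment minutes). One visit, named here, is the main comparison. Median minutes will be reported by arm and visit. The condition x time ANOVA will be used to describe change and maintenance.

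If a difference in mean minutes is wanted, make raw-scale ANCOVA the test and name the rank version as the sensitivity analysis. Either choice is defensible if made in advance. Do not rely on log(minutes + 1) if zeros occur.

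Cost: a few sentences, no new data, and SPSS can run it. The budget section records three completers and 47 participants still to recruit, so on the documents' own account the change could precede nearly all the data. Downsides: the rank test gives no difference in mean minutes, and it gives up some power to raw ANCOVA if skew is mild or gamma-like.
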